8.1.3. Facial Photography

Standardized digital facial photography will be performed prior to injection of study intervention for all participants and at the times shown in the SoA (Section 1.3). Images will be taken of each participant's face from the front at rest and at maximum frown. Each site will receive documented training and instructions on taking photographs.

Conditions of photography will be standardized across all photographs, including camera equipment, exposure, background, lighting, and focal length. Ideally, the same photographer will take all required photographs. A qualified third-party vendor will provide instructions for taking photographs and processing digital photographs. All digital images will be transferred to the sponsor at the end of the study.

Photographs will be taken for research purposes, and may also be used for education, commercial, and/or marketing purposes. To participate in this study, the participant must consent to having photographs taken for research but may still participate if he/she declines use of the photographs for other purposes. The sponsor shall have full ownership rights to any photographs derived from the study.

8.2. Safety Assessments

Planned timepoints for all safety assessments are provided in the SoA.

AGN-151586

8.2.1. Adverse Events

The investigator will question the participant to ascertain whether any adverse events were experienced since the previous visit. Additionally, the participants will be observed for at least 30 minutes following study intervention. All pertinent information regarding adverse events (ie, date of onset and stop date, duration, outcome, seriousness, severity, relationship to study intervention, treatment required, action taken with study intervention, etc) will be obtained and recorded in the source documents and appropriate eCRF page.

8.2.2. Physical Examinations

A full physical examination will be conducted at the Screening Visit and at the End-of-Study/Early Exit Visit and includes the assessment of general appearance, HEENT, heart/cardiovascular function, lungs, abdomen, extremities, back, musculoskeletal function, lymphatic function, neurologic function, and skin. *Abbreviated physical examinations* will be conducted throughout the study as described in the SoA and limited to an examination of general appearance, heart, lungs, and abdomen.

Before study intervention, if the physical examination finding is clinically significant, the finding must be captured in the medical history eCRF. After study intervention, if the pre-existing finding becomes worse and is clinically significant or the new physical examination finding is clinically significant, it must be captured as an adverse event in the adverse event eCRF.

8.2.3. Neurologic Assessment

The neurologic assessment comprises 2 elements, a Focused Symptoms Questionnaire and Focused Neurologic Examination that will be performed by trained physician investigators as described in the SOA. The neurologic assessment must be performed prior to randomization on Day 1, and is to be performed after adverse event assessment at all subsequent timepoints. See Appendix 8 for instructions for both elements.

Participants with any abnormal findings at Screening or Day 1 (prior to randomization), which meet exclusion criteria or may impact a participant's safety or the interpretation of efficacy, will be excluded from the study. For participants who meet the inclusion/exclusion criteria, images of the face at natural smile and at rest will be captured at Day 1 (prior to randomization) in order to document baseline gross facial symmetry. These images will be referenced for the Focused Neurologic Examination.

8.2.4. Vital Signs

Vital signs will be assessed as follows:

- Pulse rate (beats per minute): Participants are to be seated for at least 2 minutes, and pulse rate will be counted over 60 seconds and recorded in the source document and eCRF as beats per minute.
- Blood pressure (mm Hg): Participants are to be seated for at least 2 minutes, and systolic/diastolic blood pressure will be measured.

AGN-151586

- Respiration rate (breaths per minute): Participants are to be seated for at least 2 minutes, and breaths will be counted for 30 seconds and multiplied by 2.
- When applicable, vital sign data will be collected prior to blood draws.
- Body temperature will be taken.

Before study intervention, if the vital sign finding is clinically significant, it must be captured in the medical history eCRF. After study intervention, if the pre-existing finding becomes worse and is clinically significant or the new vital sign finding is clinically significant, it must be captured as an adverse event in the adverse event eCRF.

8.2.5. Electrocardiograms

- All participants will undergo conventional 12-lead ECG using standardized equipment and electrode placement at the visits outlined in the SoA. Participants are to be in a semirecumbent position for at least 10 minutes prior to starting the tracing. During screening, a 12-lead ECG trace will be taken to assess entry eligibility.
- A qualified third-party vendor will read the ECGs and report the findings as normal, abnormal, or unable to evaluate.
- For screening ECGs, prespecified significant abnormal findings will be flagged as exclusion alerts, and a third-party vendor will generate an exclusion alert for the site and the sponsor. Exclusion alerts are considered exclusionary for study eligibility (see Exclusion Criterion 1.05 in Section 5.2 which excludes any participant with a 'clinically significant ECG abnormality at the Screening Visit'). For all subsequent ECGs, a qualified third-party vendor will also report the appearance of any new, prespecified significant abnormal findings and generate a protocol alert for the site and the sponsor.
- The cardiologists will be blinded to participant study intervention assignments. If the ECG finding is abnormal, they will specify the abnormality or give a diagnosis, whenever it is possible. Electrocardiogram reports will be provided to the investigator and the sponsor via a secure portal within 24 hours of screening and within 72 hours for all other visits.
- Before study intervention, if the ECG finding is clinically significant, it must be captured in the medical history eCRF. After study intervention, if the pre-existing finding becomes worse and is clinically significant or the new ECG finding is clinically significant, it must be captured as an adverse event in the adverse event eCRF. Hard copies of the ECG tracings will be kept in the study files at the investigator's site.
- The ECG will be assessed for the following: heart rate, QRS duration, QT interval, QTcB interval, QTcF interval, ST segment, RR interval, PR interval, and qualitative results.

8.2.6. Clinical Safety Laboratory Assessments

• See Appendix 2 for the list of clinical laboratory tests to be performed and the SoA for the timing and frequency.

AGN-151586

- At screening, the investigator will assess the clinical significance of any values outside the reference ranges provided by the laboratory, and participants with abnormalities judged to be clinically significant will be excluded from the study.
- The investigator must review the laboratory report, document this review, and record any clinically relevant changes occurring during the study in the adverse event section of the eCRF. The laboratory reports must be filed with the source documents. Clinically significant abnormal laboratory findings are those which are not associated with the underlying disease, unless judged by the investigator to be more severe than expected for the participant's condition.
- All laboratory tests with values considered clinically significant during participation in the study, including the End-of-Study/Early Exit Visit, should be repeated until the values return to normal or baseline or are no longer considered clinically significant by the investigator or MSP.
 - If such values do not return to normal/baseline within a period of time judged reasonable by the investigator, the etiology should be identified and the sponsor notified.
 - o All protocol-required laboratory assessments, as defined in Appendix 2, must be conducted in accordance with the laboratory manual and the SoA.
 - o If laboratory values from nonprotocol specified laboratory assessments performed at the institution's local laboratory require a change in participant management or are considered clinically significant by the investigator (eg, SAE or adverse event or dose modification), then the results must be recorded in the eCRF.

8.2.7. Urine Pregnancy Test

Urine dipstick kits will be used to conduct pregnancy tests at the timepoints specified in the SoA, or more frequently at the investigator's discretion.

8.2.8. Suicidal Risk Monitoring

Suicidal risk monitoring is not applicable for this study.

8.3. Adverse Events and Serious Adverse Events

The definitions of an adverse event or SAE can be found in Appendix 3.

Adverse events will be reported by the participant.

The investigator and any qualified designees are responsible for detecting, documenting, and recording events that meet the definition of an adverse event or SAE and remain responsible for following up adverse events that are serious, considered related to the study intervention or study procedures, or that caused the participant to discontinue the study intervention (see Section 7).

Approval Date: 05-Jun-2020 18:45:11 (GMT)

AGN-151586

8.3.1. Time Period and Frequency for Collecting Adverse Event and Serious Adverse **Event Information**

All SAEs and adverse events from the signing of the ICF will be collected at the timepoints specified in the SoA (Section 1.3), and as observed or reported spontaneously by study participants.

🐔 Allergan

Medical occurrences that begin before the start of study intervention, but after obtaining informed consent will be recorded in the adverse event section of the eCRF and will be considered pretreatment adverse events.

All SAEs will be recorded and reported to the sponsor or designee within 24 hours, as indicated in Appendix 3. The investigator will submit any updated SAE data to the sponsor within 24 hours of it being available.

Investigators are not obligated to actively seek adverse event or SAE information after conclusion of the study participation. However, if the investigator learns of any SAE, including a death, at any time after a participant has been discharged from the study, and he/she considers the event to be reasonably related to the study intervention or study participation, the investigator must promptly notify the sponsor.

The method of recording, evaluating, and assessing causality of adverse events and SAEs and the procedures for completing and transmitting SAE reports are provided in Appendix 3.

8.3.2. **Method of Detecting Adverse Events and Serious Adverse Events**

Care will be taken not to introduce bias when detecting adverse events and/or SAEs. Open-ended and nonleading verbal questioning of the participant is the preferred method to inquire about adverse event occurrences.

8.3.3. Follow-up of Adverse Events and Serious Adverse Events

After the initial adverse event/SAE report, the investigator is required to proactively follow each participant at subsequent visits/contacts. All adverse events/SAEs will be followed until resolution, stabilization, the event is otherwise explained, or the participant is lost to follow-up (as defined in Section 7.3).

The investigator is obligated to perform or arrange for the conduct of supplemental measurements and/or evaluations as medically indicated or as requested by the sponsor to elucidate the nature and/or causality of the adverse event or SAE as fully as possible. This may include additional laboratory tests or investigations, histopathological examinations, or consultation with other health care professionals.

If a participant dies during participation in the study or during a recognized follow-up period, the investigator will provide the sponsor with a copy of any postmortem findings including histopathology.

New or updated information will be recorded in the originally completed eCRF.

AGN-151586

The investigator will submit any updated SAE data to the sponsor within 24 hours of receipt of the information.

8.3.4. Regulatory Reporting Requirements for Serious Adverse Events

- Prompt notification by the investigator to the sponsor of a SAE is essential so that legal obligations and ethical responsibilities towards the safety of participants and the safety of a study intervention under clinical investigation are met.
- The sponsor has a legal responsibility to notify both the local regulatory authority and other regulatory agencies about the safety of a study intervention under clinical investigation. The sponsor will comply with country-specific regulatory requirements relating to safety reporting to the regulatory authority, IRBs/IECs, and investigators.
- An investigator who receives an investigator safety report describing an SAE or other specific safety information (eg, summary or listing of SAEs) from the sponsor will review and then file it along with the IB and will notify the IRB/IEC, if appropriate according to local requirements.
- Investigator safety reports must be prepared for SUSARs according to local regulatory requirements and sponsor policy and forwarded to investigators as necessary.

8.3.5. Pregnancy

- Details of all pregnancies, including pregnancy outcome, in female participants and consented female partners of male participants will be collected; pregnancies include those with onset after study intervention, and until 10 weeks after study intervention for female participants and until 6 weeks after study intervention for female partners of male participants.
- At each visit, site personnel must discuss with WOCBP and males with partners who are WOCBP compliance with contraceptive use.
- Urine pregnancy testing will be conducted for WOCBP at the Screening Visit, prior to randomization at Day 1, at the study exit visit, and at the discretion of the investigator. See Appendix 7 for detailed information on definition of WOCBP, use of contraceptives, and pregnancy.
- Women who test positive for urine pregnancy test prior to randomization will NOT receive treatment and will be discontinued from the study.
- If a pregnancy is confirmed after the participant has received study intervention, the participant may choose to exit the study after appropriate safety follow-up or remain in the study for all safety and efficacy follow-up assessments.
- Any termination of pregnancy will be reported, regardless of fetal status (presence or absence of anomalies) or indication for the procedure.

AGN-151586

- If a pregnancy is reported, the investigator should inform the sponsor within 24 hours of learning of the pregnancy and should follow the procedures outlined in Appendix 7.
- Abnormal pregnancy outcomes (eg, spontaneous or elective abortion, fetal death, stillbirth, congenital anomalies, ectopic pregnancy) or genetic abnormalities (whether leading to an elective abortion or not) are considered SAEs.

8.3.6. Adverse Events of Special Interest

There are no AESIs for this study because they are not clinically indicated.

8.3.7. Medication Errors

Medication error refers to any unintended error in the dosing and/or administration of the study intervention as per instructions in the protocol. Medication errors generally fall into 4 categories as follows:

- Wrong study intervention
- Wrong dose (including dosing regimen, strength, form, concentration, amount)
- Wrong route of administration
- Wrong participant (ie, not administered to the intended participant)

Medication errors include occurrences of overdose and underdose of the study intervention.

Overdose: Unintentional administration of a quantity of the study intervention given per administration that is above the maximum recommended dose according to the protocol for the study intervention. See Section 8.4 for information of treatment of overdose.

Underdose: Unintentional administration of a quantity of the study intervention given per administration that is under the minimum recommended dose according to the protocol.

8.4. Treatment of Overdose

Overdose of AGN-151586 is a relative term and depends upon dose, site of injection, and underlying tissue properties. Signs and symptoms of overdose are likely not to be apparent immediately postinjection. Excessive doses may produce local, or distant, generalized and profound neuromuscular paralysis.

Because AGN-151586 is administered as injections by physicians, for this study, the chance of overdose is extremely low. Should accidental injection occur or overdose be suspected, the participant should be medically monitored for up to several weeks for progressive signs or symptoms of systemic muscular weakness that could be local or distant from the site of injection, which may include ptosis, diplopia, dysphagia, dysarthria, generalized weakness, or respiratory failure. Eyelid ptosis, diplopia, or vision blurred are known local effects of BoNT/A during treatment of glabellar lines, which may also occur with BoNT/E. These participants should be considered for further medical evaluation and appropriate medical therapy immediately instituted, which may include hospitalization.

AGN-151586

If the musculature of the oropharynx and esophagus is affected, aspiration may occur, which may lead to development of aspiration pneumonia. If the respiratory muscles become paralyzed or sufficiently weakened, intubation and assisted respiration may be necessary until recovery takes place. Supportive care could involve the need for a tracheostomy and/or prolonged mechanical ventilation, in addition to other general supportive care.

In the event of an overdose, the investigator should:

- 1. Contact the MSP immediately.
- 2. Closely monitor the participant for any AE/SAE.
- 3. Document the quantity of the excess dose in the eCRF.

8.5. Pharmacokinetics

Pharmacokinetic parameters are not evaluated in this study.

8.6. Pharmacodynamics

Pharmacodynamic parameters are not evaluated in this study.

8.7. Genetics

Genetics are not evaluated in this study.

8.8. Biomarkers and Other Assessments

Immunogenicity Assessments

Validated assays will be used to assess the presence of antidrug antibodies to AGN-151586, using blood samples collected during the course of the study.

Blood samples for immunogenicity testing will be collected from each participant at Screening, and at the Day 7, Day 28, and End-of-Study visits. Collected samples (approximately 20 mL per sample) will be processed to yield serum for analysis.

Detection of binding antibodies against AGN-151586 in participants' serum will be carried out using the validated ELISA in a 3-tier format (screening, confirmation, and titering). Only samples that are confirmed positive in the confirmatory assay will be stored and analyzed for presence of neutralizing antibodies to AGN-151586 when a validated assay becomes available.

These samples may also be used for additional characterization of antibody response to other neurotoxin subtype(s). The findings from this exploratory analysis will be documented in the clinical study report or in a separate report. The ICF will contain a separate appendix that addresses the use of immunogenicity samples for this optional exploratory research. The investigator or his/her representative will explain to each participant that their participation is voluntary. With regards to using their blood samples for this exploratory characterization of antibody response to other neurotoxin subtype(s), participants may give consent, refuse to give consent, or may give consent and later withdraw their consent at any time and for any reason

AGN-151586

during the storage period. A separate signature will be required to document a participant's agreement or refusal to allow specimens to be used for this exploratory research.

8.9. Medical Resource Utilization and Health Economics

Medical resource utilization and health economics parameters are not evaluated in this study.

9. Statistical Considerations

9.1. Statistical Hypotheses

The following hypotheses will be used to compare each dose group of AGN-151586 with placebo:

- Null hypothesis: AGN-151586 and placebo are equally effective in the probability of reducing GL severity at maximum frown as measured by $a \ge 2$ -grade improvement from baseline based on the investigator-rated FWS at any posttreatment timepoint through Day 7.
- Alternative hypothesis: AGN-151586 and placebo are not equally effective in the probability of reducing GL severity at maximum frown as measured by a ≥ 2-grade improvement from baseline based on the investigator-rated FWS at any posttreatment timepoint through Day 7.

9.2. Sample Size Determination

For each cohort, there will be approximately 40 participants (AGN-151586: n = 30; placebo: n = 10) with a 3:1 randomization allocation; up to 5 dose cohorts are planned. For a cohort of 30 participants treated with AGN-151586, there is an approximately 60% chance of detecting an adverse event which occurs at a 3% incidence (eg, eyelid ptosis).

Approximately 200 participants will be randomized to have approximately 180 participants complete the study based on an anticipated dropout rate of 10%. Approximately 150 participants are expected to have a single dose exposure to AGN-151586 with an approximately 78% chance to detect any adverse event at a 1% incidence, and a 95% chance to detect any adverse event at a 2% incidence.

The primary efficacy analysis will be conducted on the mITT population, which consists of randomized participants who have been dosed and have a posttreatment measurement of investigator-rated FWS at maximum frown. A sample size of 40 participants per cohort will have approximately 87% power to detect a difference between an AGN-151586 dose group and the placebo group, assuming a 10% dropout rate and responder rates of 70% for the AGN-151586 study intervention group and 10% for the placebo group.

The calculation is based on a 2-sided Chi-squared test (Fisher's exact test) with a 0.05 significance level using nQuery Advisor version 7.0.

9.3. Populations for Analyses

For the efficacy analyses, the mITT population will be used and include all randomized participants who received study intervention and who had a posttreatment investigator-rated FWS measurement at maximum frown. The safety analysis will be performed using the safety population that includes all participants who received study intervention. All analyses will be performed on an as-treated basis.

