**Estimand Framework:**

Objective	Clinical Category	Statistical Category	Estimand/Variable
Primary Objectives:			
			

• Efficacy: To compare the efficacy between placebo and a range of doses of AGN-151586 for the treatment of glabellar lines (GL) in participants with moderate to severe GL

• Safety: To compare the safety between placebo and a range of doses of AGN-151586 for the treatment of GL in participants with moderate to severe GL

Effectiveness 	Primary		

• Variable: Achievement of a <math>\geq 2</math> grade improvement from baseline on the Facial Wrinkle Scale (FWS) With Photounumeric Guide according to investigator assessments of GL severity at maximum frown at any postintervention timepoint through Day 7

• Population: The target population is the randomized population that has met the inclusion and exclusion criteria; the analysis population is the modified intention-to-treat (mITT) population (randomized participants who have received study intervention and have at least one postintervention measurement of investigator-rated FWS at maximum frown)

• IES: Participants with no valid assessments at any postintervention timepoint through Day 7 will be excluded from the analysis

• PLS: Response rates between each dose group of AGN-151586 and placebo

• Analysis: Cochran-Mantel-Haenzsel (CMH) test stratified by baseline GL severity at maximum frown (investigator assessment), using observed data without imputation or adjustment for multiplicity. Between group comparisons will only be performed for each cohort's AGN-151586 group against the cohort's placebo group. Nominal p-values will be presented for each statistical test.

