**Table 4-1 Analysis Populations**

Population	Definition	Study Intervention
mITT Population	All randomized participants who receive study intervention and who have at least one postintervention investigator-rated FWS measurement at maximum frown	As treated
Safety Population	All participants who receive study intervention	As treated

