## 5. Statistical Analyses

### 5.1. General Considerations

- The primary analyses will be performed after the database is locked and randomization schedule is released.
- The effectiveness endpoints will be analyzed based on the mITT Population. Safety analyses will be performed using the Safety Population. The analyses will be based on the actual study intervention that the participants receive.
- For each cohort, the effectiveness and safety endpoints will be analyzed/summarized by study intervention group, i.e., AGN-151586 group and placebo group, respectively. In addition, placebo groups across cohorts will be pooled to compare with each dose of AGN-151586 group as a sensitivity analysis.
- For applicable effectiveness and safety endpoints, baseline is defined as the last non-missing assessment prior to study intervention.
- Descriptive statistics for continuous variables include the sample size (N), mean, standard deviation, median, 1st and 3rd quartiles, minimum, and maximum. Summary statistics for categorical variables include the sample size (N), frequency count, and percentage.
- The primary analysis of the effectiveness endpoint, ie, the response rate of the participants with achievement of a  $\geq 2$  grade improvement from baseline on the FWS according to investigator assessments of GL severity at maximum frown at any postintervention timepoint through Day 7, will be analyzed using CMH tests stratified by baseline GL severity at maximum frown, to compare the between-group difference. The observed data without imputation will be used. Nominal p-values will be provided for each statistical testing. No multiplicity adjustment will be performed to control overall type I error.
- Summary of TEAEs, medical history, and concomitant medication will be summarized by study intervention group for each cohort. Also, the AGN-151586 groups across cohorts and the placebo groups across cohorts will be pooled.
- Partial dates will be treated as missing in computations, and will be listed in the data listings as they appear on the electronic case report form (eCRFs). No imputation of missing values will be performed, unless otherwise specified.
- The level of significance used for statistical testing of the effectiveness endpoints will be 0.05, 2-sided.

- The change from baseline values will be computed as the value for the postbaseline visit minus the baseline value.

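### Primary efficacy in the mITT population is grouped by product received, and no planned analysis compares the arms as randomised; a cheap wording change would fix this

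*Protocol*

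**What the plan says.** Protocol 9.3 says that for efficacy "the mITT population will be used and include all randomized participants who received study intervention and who had a posttreatment investigator-rated FWS measurement"; the rating meant is the one made while frowning maximally. It assigns safety to all who received study intervention, and then adds one rule for both sets: "All analyses will be performed on an as-treated basis".

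The SAP keeps the rule. SAP 5.1 names mITT for effectiveness and Safety for safety, and continues: "The analyses will be based on the actual study intervention that the participants receive". In SAP Table 4-1 the mITT definition begins "All randomized participants who receive study intervention", and the study-intervention column reads as treated for mITT as well as for Safety. SAP 6.2 lists one change to the protocol-planned analyses, TEAEs in place of AEs, so the grouping rule was carried over unchanged.

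The primary test is a CMH test stratified by baseline severity, the randomisation stratification factor. It compares each cohort's active group with that cohort's own placebo group (SAP 1.1 and 5.3.2). The additional analyses of the primary endpoint in SAP 5.3.2 and 5.3.3 are non-responder imputation and pooled placebo. Neither regroups participants as randomised.

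**The concern.** Randomisation within severity strata makes the assigned groups comparable. Groups formed by the product actually given are defined after randomisation and do not carry the same guarantee. Grouping as treated is the usual choice for safety. For efficacy, the usual primary comparison is by assigned arm, and a set labelled modified intent-to-treat leads a reader to expect it.

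If a participant receives the wrong product, this plan shows only the as-treated result; the comparison that randomisation protects would not be reported at all. The primary comparisons are small: "For each cohort, there will be approximately 40 participants (AGN-151586: n = 30; placebo: n = 10) with a 3:1 randomization allocation". In a placebo group of 10, where one person is counted matters.

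**Working it through.** **When the two groupings differ.** Treatment is a single double-blind administration on Day 1 from identical-appearing vials, under site supervision, with no retreatment and no rescue (Protocol 6, 6.1, 6.4, 6.5.3). Crossover and non-compliance therefore cannot separate assigned from received treatment. What remains is an error that gives active for placebo or the reverse, through the wrong-intervention or wrong-participant categories of Protocol 8.3.7. The step-wise dilution described under Protocol 6.1 may make the actual dose differ slightly from the nominal dose. That is variation inside the active arm and moves nobody between arms.

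**Inputs.** 30 active and 10 placebo per cohort; "assuming a 10% dropout rate and responder rates of 70% for the AGN-151586 study intervention group and 10% for the placebo group"; Fisher's exact test, two-sided, at the 0.05 level (all Protocol 9.2).

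**The plan's own figure.** Evaluable: 30 × 0.9 = 27 and 10 × 0.9 = 9. Exact enumeration of Fisher's test for 27 against 9, at 0.70 against 0.10 with 0.025 in each tail, gives 87.2%. The protocol states about 87%, so it reproduces. The SAP's 88% at 5% dropout reproduces with 28 against 9 (88.3%). The grouping rule leaves these figures unchanged when there are no errors.

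**Expected difference as randomised after wrong-product errors.** The documents give no error rate, so the counts below are assumed scenarios per cohort, and response is assumed to follow the product received. With a active-assigned participants given placebo and b placebo-assigned participants given active:

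- active rate = [0.70 × (27 − a) + 0.10 × a] / 27
- placebo rate = [0.10 × (9 − b) + 0.70 × b] / 9

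| a, b | Active | Placebo | Difference as randomised | Power as randomised | Power as treated |
|---|---|---|---|---|---|
| 0, 0 | 70.0% | 10.0% | 60.0 points | 87.2% | 87.2% |
| 1, 0 | 18.3/27 = 67.8% | 10.0% | 57.8 | 84.3% | 90.3% (26 vs 10) |
| 0, 1 | 70.0% | 1.5/9 = 16.7% | 53.3 | 74.0% | 83.1% (28 vs 8) |
| 1, 1 | 67.8% | 16.7% | 51.1 | 69.1% | 87.2% (27 vs 9) |
| 2, 2 | 17.7/27 = 65.6% | 2.1/9 = 23.3% | 42.2 | 43.4% | 87.2% (27 vs 9) |

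Under the same assumption the expected as-treated difference stays at 60 points in every row. Power is for the unstratified Fisher test used in planning, not the stratified CMH test.

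**What one case does to observed rates.** Illustration only, without dropout: suppose 21/30 active-assigned and 2/10 placebo-assigned participants respond, and one placebo-assigned participant was given active.

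- As randomised: 21/30 = 70.0%, 2/10 = 20.0%, difference 50.0 points.
- As treated, if that participant responded: 22/31 = 71.0%, 1/9 = 11.1%, difference 59.9 points.
- As treated, if that participant did not respond: 21/31 = 67.7%, 2/9 = 22.2%, difference 45.5 points.

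One person moves the placebo rate down by 8.9 points or up by 2.2 points, so the direction is not fixed. The 20% starting rate is chosen for the example; the plan assumes 10%.

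**The case against.** The case for leaving the plan alone is fair. The rule is stated consistently in both documents and looks deliberate. The trial explores dose, so grouping by what was injected has a rationale. P-values are nominal, with no multiplicity adjustment. With one blinded, supervised injection, wrong-product errors should be rare. The table above also shows dilution under as-randomised grouping; it shows no distortion under the current rule. All of this stands, and it limits the weight of the point. It does not explain why the randomised comparison is never shown.

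A reader might infer more than the documents support, in four ways:

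- **That the rule breaks the randomised comparison or biases the result.** Without a wrong-product error the groupings coincide. If an error made under blinding is unrelated to prognosis, the as-treated groups may stay comparable. No bias or Type I error inflation has been shown.
- **That any misallocation would have a non-random cause.** Nothing in the documents shows this. The section on randomisation and blinding (Protocol 6.3) is not in the public text, so the safeguards cannot be judged.
- **That site dilution errors would move people between arms.** They change dose, not arm.
- **That the estimand contradicts the grouping rule.** The SAP estimand table says "The target population is the randomized population that has met the inclusion and exclusion criteria". That describes who is studied, not how they are grouped, and the same entry names mITT as the analysis population. The mismatch is one of label and expectation.

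**Conclusion.** The point holds as a cheap improvement. The primary efficacy analysis is grouped by product received, and no visible analysis compares the arms as randomised. The expected effect is small, and zero if every participant receives the assigned product. One wrong-product case in a cohort can shift a placebo rate of about 10 participants by several points, in either direction. The sizes given rest on assumed error counts, on response following the product received, and on the planning rates of 70% and 10%. The documents do not support a claim that the planned result is biased. The mITT requirement of dosing and a post-treatment rating is a separate post-randomisation exclusion, which this point does not address.

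**What to change.** In Protocol 9.3, SAP Table 4-1 and SAP 5.1, state that the mITT population is analysed by assigned arm and randomisation stratum, and that the Safety population is analysed as treated. Add to SAP 5.3.3 that, if any participant receives a product other than the one assigned, efficacy as treated will be reported as a sensitivity analysis. Record the change in SAP 6.2. Settle it before the randomisation schedule is released, so that the grouping is not chosen with knowledge of the errors.

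The cost is wording in both documents, with no new data and no loss of power if no error occurs. The downside arises only if one does: the as-randomised difference is then diluted, for example from 60.0 to 51.1 points for one swap each way in a cohort. The as-treated sensitivity analysis would show the result by product received alongside it.
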